7.4.1.1 Definitions

Definition of adverse event (AE)

In a clinical study, an AE is any untoward medical occurrence (i.e. any unfavorable and unintended sign [including abnormal laboratory findings], symptom or disease) in a patient or clinical investigation subject after providing written informed consent for participation in the study. Therefore, an AE may or may not be temporally or causally associated with the use of a medicinal (investigational) product.

A surgical procedure that was planned prior to the start of the study by any physician treating the subject should not be recorded as AE (however, the condition for which the surgery is required may be an AE if the condition worsens compared to baseline).

- Conditions that started before signing of informed consent and for which no symptoms or treatment are present until signing of informed consent are recorded as medical history (e.g. seasonal allergy without acute complaints).
- Conditions that started before signing of informed consent and for which symptoms or treatment are present after signing of informed consent, at *unchanged intensity*, are recorded as medical history (e.g. phantom pain).
- Conditions that started or deteriorated after signing of informed consent will be documented as adverse events.

Definition of serious adverse event (SAE)

An SAE is classified as any untoward medical occurrence that, at any dose, meets any of the following criteria (a – f):

- a. Results in death.
- b. Is life-threatening.

The term 'life-threatening' in the definition refers to an event in which the patient was at risk of death at the time of the event, it does not refer to an event which hypothetically might have caused death if it were more severe.

- c. Requires inpatient hospitalization or prolongation of existing hospitalization.

A hospitalization or prolongation of hospitalization will not be regarded as an SAE if at least one of the following exceptions is met:

- The admission results in a hospital stay of less than 12 hours.
- The admission is pre-planned.
(i.e. elective or scheduled surgery arranged prior to the start of the study)
- The admission is not associated with an AE.
(e.g. social hospitalization for purposes of respite care).

However, it should be noted that invasive treatment during any hospitalization may fulfill the criterion of 'medically important' and as such may be reportable as an SAE dependent on clinical judgment. In addition, where local regulatory authorities specifically require a more stringent definition, the local regulation takes precedence.

- d. Results in persistent or significant disability / incapacity.

Disability means a substantial disruption of a person's ability to conduct normal life's functions.

- e. Is a congenital anomaly / birth defect.

- f. Is another medically important serious event as judged by the investigator.

7.4.1.2 Classifications for adverse event assessment

- Study treatment action
- Other specific treatment of AE
- Causal relationship to protocol-required procedures(s)
- Outcome

All unexpected and related grade 3 and 4 AEs will be assessed and documented in the MDACC AE log by the investigator according to the categories detailed below.

The Investigator or physician designee is responsible for verifying and providing source documentation for all adverse events and assigning the attribution for each event for all subjects enrolled on the trial.

7.4.1.2.1 Seriousness

An adverse event or suspected adverse reaction is considered “serious” if, in the view of either the investigator or the sponsor, it results in any of the following outcomes:

- Death
- A life-threatening adverse drug experience
- Any adverse experience that places the patient, in the view of the initial reporter, at immediate risk of death from the adverse experience as it occurred. It does not include an adverse experience that, had it occurred in a more severe form, might have caused death
- Inpatient hospitalization or prolongation of existing hospitalization
- A persistent or significant incapacity or substantial disruption of the ability to conduct normal life functions
- A congenital anomaly/birth defect

Important medical events that may not result in death, be life-threatening, or require hospitalization may be considered a serious adverse drug experience when, based upon appropriate medical judgment, they may jeopardize the patient or subject and may require medical or surgical intervention to prevent one of the outcomes listed in this definition. Examples of such medical events include allergic bronchospasm requiring intensive treatment in an emergency room or at home, blood dyscrasias or convulsions that do not result in inpatient hospitalization, or the development of drug dependency or drug abuse (21 CFR 312.32).

Important medical events as defined above may also be considered serious adverse events. Any important medical event can and should be reported as an SAE if deemed appropriate by the Principal Investigator or the IND Sponsor, IND Office.

All events occurring during the conduct of a protocol and meeting the definition of a SAE must be reported to the IRB in accordance with the timeframes and procedures outlined in “University of Texas M. D. Anderson Cancer Center Institutional Review Board Policy for investigators on Reporting Serious Unanticipated Adverse Events for Drugs and Devices”. Unless stated otherwise in the protocol, all SAEs, expected or unexpected, must be reported to the IND Office, regardless of attribution (within 5 working days of knowledge of the event).

- **All life-threatening or fatal events**, that are unexpected, and related to the study drug, must have a written report submitted within **24 hours** (next working day) of knowledge of the event to the Safety Project Manager in the IND Office.

Unless otherwise noted, the electronic SAE application (eSAE) will be utilized for safety reporting to the IND Office and MDACC IRB.

- **Serious adverse events will be captured from the time of the first protocol-specific intervention, until 30 days after the last dose of drug, unless the participant withdraws consent. Serious adverse events must be followed until clinical recovery is complete and laboratory tests have returned to baseline, progression of the event has stabilized, or there has been acceptable resolution of the event.**
- **Additionally, any serious adverse events that occur after the 30 day time period that are related to the study treatment must be reported to the IND Office. This may include the development of a secondary malignancy.**

Reporting to FDA:

- **Serious adverse events will be forwarded to FDA by the IND Sponsor (Safety Project Manager IND Office) according to 21 CFR 312.32.**

It is the responsibility of the PI and the research team to ensure serious adverse events are reported according to the Code of Federal Regulations, Good Clinical Practices, the protocol guidelines, the sponsor's guidelines, and Institutional Review Board policy.

For each AE, the seriousness must be determined according to the criteria given in Section 7.4.1.1.

7.4.1.2.2 Intensity

The intensity of the AE is classified according to the CTCAEv4.0. Grade refers to the severity (intensity) of the AE:

CTCAEv4 Grade 3: Severe or medically significant but not immediately life threatening; hospitalization or prolongation of hospitalization is indicated; disabling; limiting to self care ADL (self care ADL refers to bathing, dressing and undressing, feeding self, using the toilet, taking medications, and not bedridden).

CTCAEv4 Grade 4: life-threatening consequences; urgent intervention is indicated.

CTCAEv4 Grade 5: death due to an AE.

7.4.1.2.3 Causal relationship

The assessment of the causal relationship between an AE and the administration of treatment is a clinical decision based on all available information.

The causality assessment should be done separately for each study treatment.

The assessment is based on the question whether there was a “reasonable causal relationship” to the study treatment in question.

Possible answers are “yes” or “no”.

An assessment of “no” would include:

1. The existence of a clear alternative explanation, e.g. mechanical bleeding at surgical site.
- or
2. Non-plausibility, e.g. the subject is struck by an automobile when there is no indication that the drug caused disorientation that may have caused the event; cancer developing a few days after the first drug administration.

An assessment of “yes” indicates that there is a reasonable suspicion that the AE is associated with the use of the study treatment.

Factors to be considered in assessing the relationship of the AE to study treatment include:

- The temporal sequence from drug administration: The event should occur after the drug is given. The length of time from drug exposure to event should be evaluated in the clinical context of the event.
- Recovery on drug discontinuation (de-challenge), recurrence on drug re-introduction (re-challenge):
- Subject’s response after de-challenge or subjects response after re-challenge should be considered in the view of the usual clinical course of the event in question.
- Underlying, concomitant, intercurrent diseases:
Each event should be evaluated in the context of the natural history and course of the disease being treated and any other disease the subject may have.
- Concomitant medication or treatment:
The other drugs the subject is taking or the treatment the subject receives should be examined to determine whether any of them may be suspected to cause the event in question.

- The pharmacology and pharmacokinetics of the study treatment:
The pharmacokinetic properties (absorption, distribution, metabolism and excretion) of the study treatment, coupled with the individual subject's pharmacodynamics should be considered.

[Causal relationship to protocol-required procedure(s)]

The assessment of a possible causal relationship between the AE and protocol-required procedure(s) is based on the question whether there was a “reasonable causal relationship” to protocol-required procedure(s).

Possible answers are “yes” or “no”.

7.4.1.2.4 Action taken with study treatment

Any action on study treatment to resolve the AE may be documented using the categories listed below.

- Drug withdrawn
- Drug interrupted
- Dose reduced
- Dose not changed
- Dose increased
- Not applicable
- Unknown

7.4.1.2.5 Other specific treatment(s) of adverse events

- None
- Remedial drug therapy
- Other

7.4.1.2.6 Outcome

The outcome of the AE may be documented as follows:

- Recovered/resolved
- Recovering/resolving
- Recovered/resolved with sequelae
- Not recovered/not resolved
- Fatal
- Unknown

7.4.1.3 Assessments and documentation of adverse events

7.4.1.4 Reporting of serious adverse events

The definition of serious adverse events (SAEs) is given in Section 7.4.1.1.

Each serious adverse event must be followed up until resolution or stabilization, by submission of updated reports to the designated person. An isolated laboratory abnormality that is assigned grade 4, according to CTC definition, is not reportable as an SAE; unless the investigator assesses that the event meets standard ICH criteria for an SAE. CTC grade 4 baseline laboratory abnormalities that are part of the disease profile should not be reported as an SAE, specifically when they are allowed or not excluded by the protocol inclusion/exclusion criteria.

When required, and according to local law and regulations, serious adverse events must be reported to the Ethics Committee and Regulatory Authorities.

All serious and unexpected adverse events should be reported to MD Anderson IRB and Bayer within 24 hours. In the event of such an event, the investigator should refer to the Pharmacovigilance section of the contract for reporting procedures.

The Investigator may report serious adverse drug reactions (SADRs) using either:

An ADEERS form (Adverse Event Expedited Reporting System) available at <http://ctep.cancer.gov/reporting/adeers.html>

OR

A MedWatch form available at <http://www.fda.gov/medwatch/>

All reports shall be sent electronically to:

Electronic Mailbox: [contact]

[contact]

Address: Global Pharmacovigilance - USA
Mail only: Bayer HealthCare
[name]
[name]

Address: [name]
FDX or UPS only [name]

Reports for all Bayer products can also be phoned in via our Clinical Communications Dept:

[contact]

7.4.1.5 Expected adverse events

For this study, the applicable reference document is the most current version of the investigator's brochure (IB) / summary of product characteristics.

Overview listings of frequent events that have occurred so far in the clinical development are shown in the current IB. If relevant new safety information is identified, the information will be integrated into an update of the IB and distributed to all participating sites.

The expectedness of AEs will be determined by the study physician according to the applicable reference document and according to all local regulations.

7.4.1.6 Adverse events of special safety interest:

Since radium 223 dichloride is eliminated in the feces, but is an alpha emitter, feces containing the radiopharmaceutical can be safely disposed of by flushing down the toilet. If however there is ever an incident of placing the subjects excreta in the food of another person and the radiopharmaceutical is ingested (e.g. an alpha particle emitting special sandwich), this should be reported to the principal investigator and the principal investigator or designate should then determine whether the oral ingestion poses any safety risk (probably not) using gamma camera imaging to quantitate whether any significant bone absorption has occurred.

Long-term growth monitoring (<18 years only)

Patients with growth potential (e.g. epiphysis has significant uptake on the screening $^{99m}\text{TcMDP}$ scan) will have yearly growth monitored (and compared to weight and height vs weight percentile) for age until age 21 or no significant change of height is seen for 2 consecutive years- whichever is first.

Any secondary malignancies or potential long-term (i.e. > 2 months) grade 3 or greater hematologic toxicities will also be reported to MD Anderson IRB and Bayer.

Survival data will be reported yearly as long as MD Anderson Cancer Center IRB continuing review and yearly IND reporting is done. Data concerning any expected unexpected or unusual bone toxicities (e.g. hardware failure, pathologic fracture of limb salvage bones) will be collected and reported annually.

7.4.2 Pregnancies

The investigator must report to Bayer any pregnancy occurring in a study subject, or in his partner, during the subject's participation in this study. The report should be submitted within the same timelines as an SAE, although a pregnancy per se is not considered an SAE.

For a study subject, the outcome of the pregnancy should be followed up carefully, and any abnormal outcome of the mother or the child should be reported.

For the pregnancy of a study subject's partner, all efforts should be made to obtain similar information on course and outcome, subject to the partner's consent.

For all reports, the forms provided are to be used.

7.4.3 Further safety

Progressive disease

If progressive disease leads to signs and symptoms that meet the criteria for an SAE (i.e., hospitalization, disability, death, or important medical event), the signs and symptoms should be reported as an SAE and not the underlying progressive disease.

Death

If any subject dies during the trial or within 30 days of the end-of-treatment visit, the investigator will inform MD Anderson IRB and Bayer and record the cause of death in detail (using the SAE Form) within 1 working day.

7.5 Other procedures and variables

7.6 Appropriateness of procedures / measurements

The assessments described in the previous sections are widely used and generally recognized as reliable, accurate, and relevant for determining the safety and efficacy of therapies in osteosarcoma.

8. Statistical methods and determination of sample size

8.1 Analysis sets

Safety monitoring rule

- Should DLTs occur in more than two patients at any time during the dose expansion phase clinical personnel and study investigators will meet and assess the attribution, severity and nature of the DLTs. No additional patients will be accrued until the data is reviewed and a decision is made to continue at the current dose or to de-escalate the prior dose as the dose for the expansion phase. This review and decision will be documented in writing.

Monitoring of alkaline phosphatase

- Alkaline phosphatase, a biomarker associated with osteosarcoma metastases, will be determined monthly before administration of each dose of Ra-223 dichloride. The trend of improvement (or not) will be analyzed for a particular patient and number of patients in a cohort with improvement as a function of dose # will be analyzed.

Imaging

- Nuclear Medicine Studies will use commercially available ^{99m}Tc , ^{18}F Fluorodeoxyglucose and sodium ^{18}F Fluoride to image indicator lesions. The trend of improvement (or not) in ^{99m}Tc -MDP on SPECT CT, ^{18}F FDG-PET-CT SUV, or Na^{18}F SUV will be compared for study entry vs after dose #3 and study entry vs after dose #6 and after dose #3 vs after dose #6 will analyzed for a particular patient and number of patients in a cohort with improvement after dose #3 and dose #6 will be analyzed.
- Analysis of lung metastases. Up to 3 measurable (1 cm or larger) indicator lesions seen on chest CT may be described at study entry and compared after dose #3 and dose #6. RECIST criteria (>20% increase in size) will be used as criteria for progression. Any change <20% or if size is <1 cm will not be used for “off study” progression criteria.
- RECIST progression will determine progressive disease regardless of other imaging.

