1.1 Background

Ra-223 dichloride is potentially a very low toxicity and high efficacy targeted agent for osteosarcoma, an osteoblastic bone-forming tumor. Because of low marrow toxicity of this radiopharmaceutical, knowledge of the MTD in this patient population is needed to develop future protocols. Use of Ra-223 dichloride in osteosarcoma should reduce the morbidity of therapy and mortality from metastases. The goal of this initial study is to determine the safety of escalating doses of monthly $^{223}\text{RaCl}_2$ in osteosarcoma patients with osteoblastic bone-forming metastases until MTD or a dose 100 kBq/kg dose is reached (whichever is first). Ra-223 dichloride will be given monthly and side effects of this bone-targeted therapy on monthly blood counts and alkaline phosphatase will be determined. After 3 and 6 doses patients will have imaging to compare $^{99\text{m}}\text{TcMDP}$ uptake to baseline and other imaging as clinically indicated including ^{18}F -FDG PET-CT, Na^{18}F and/ chest CT. Evaluations will include anatomic imaging (CT or MRI) of all sites of disease along with chest CT at baseline and restaging for all patients to allow for assessment of RECIST progression. RECIST progression will determine progressive disease regardless of other imaging. If well tolerated at the MTD, an additional 6 patients will be studied to better define toxicity and obtain data to support future investigation of Ra-223 dichloride with other agents and modalities (e.g. other drugs, surgery or external beam RT) for improved treatment of osteosarcoma.

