beforehand and given suitable personal protection equipment (i.e. universal blood and body fluid precautions - especially when handling ashes containing potentially radioactive bone fragments. Calculations and the rationale for radiation dose estimates are available upon request (see investigators Brochure).

Definition of Dose-Limiting Toxicities (DLTs):

Toxicities will be graded in severity according to the guidelines outlined in the NCI Common Terminology Criteria for Adverse Events (CTCAE) version 4.0 (publish date 28-May-2009). Dose-limiting toxicities include all adverse experiences that are related to study medication, and clearly not related to disease progression or intercurrent illness.

Based on prior experience with other bone seeking radiopharmaceuticals and Ra-223 dichloride in prostate cancer patients, the expected dose limiting toxicity (DLT) will be hematologic. Lymphopenia is common in patients with bone metastases and will be monitored, but not considered a DLT in this protocol. Any grade 4 anemia, any grade 4 neutropenia for >7 days or grade 4 neutropenia with fever (a single temperature greater than 38.3°C or a sustained temperature of $\geq 38^\circ\text{C}$ for more than one hour) and grade 3 or 4 thrombocytopenia with clinically significant bleeding will be dose limiting. Grade 3 non-hematologic toxicities except for nausea, emesis or diarrhea that are controlled with maximal medical management within 72 hours will be considered dose-limiting. DLTs will only be monitored during the first 6 weeks of treatment. Ongoing toxicity that causes a delay of more than 2 weeks in starting the next cycle will also be dose-limiting if it occurs during the first cycle.

Dose Modification and Escalation

Every effort should be made to administer the full dosing regimen of Ra-223 dichloride. Adjustment of dose level is not permitted.

- A minimum of 3 patients initially will be enrolled at the first dose level.
- If at least 2 patients are observed to have a dose-limiting toxicity (DLT), the MTD will have been exceeded and no further patients will be enrolled at this dose level or at any higher dose level. The prior dose level is defined as the MTD (unless only 3 patients have been treated at that level, in which case it is the tentative MTD).
- If 0 of the 3 patients are observed to have DLT during the DLT assessment period, the dose level is escalated one step for the next cohort of 3 patients, and the process continues as above.

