- If exactly 1 of the 3 patients treated show DLT during the DLT assessment period, 3 additional patients are treated at the current dose level.
- If none of these additional 3 patients show DLT during the DLT assessment period, the dose level is escalated for the next cohort of 3 patients, and the process continues as above; otherwise, the prior dose level is defined as the MTD (unless only 3 patients have been treated at that level, in which case it is the tentative MTD).
- A tentative MTD becomes final when a total of 6 patients are treated with less than 2 showing DLT.
- If 2 of the first 3 patients have hematologic DLT, then next cohort will be dose level -1.

Study visits during the treatment period should occur at 4 weeks intervals (within a window of +/- 7 days). **Dosing delays** may be instituted under the following circumstances:

Disease progression:

The Investigator should delay cytotoxic chemotherapy, other systemic radioisotope, hemibody external radiotherapy or other investigational drug until the follow-up period. If such treatments have to be given during the treatment period, further study drug administrations must be discontinued. Patients with disease progression may continue other treatment at the Investigator's discretion.

Myelosuppression:

Treatment-related changes in hematology parameters may occur.

- Blood transfusion is acceptable between study drug administrations. Use of biologic response modifiers, such as G-CSF or GM-CSF, is allowed in the management of acute toxicity.
- If myeloid growth factors are required for the management of acute toxicity this event should be considered a DLT.

Gastrointestinal events:

Diarrhea should be treated as per local practice. A further dose of study medication should not be given before diarrhea is recovered to CTCAE v4.03 Grade 2 or baseline levels.

Nausea or vomiting should be treated as per local practice. A further dose of study medication should not be given before nausea or vomiting is recovered to CTCAE v.4.03 Grade 2 or baseline levels.

For any grade 3 hematologic toxicity for >14 days, study drug administrations must be discontinued (grade 4 events of anemia and neutropenia >7 days are dose-limiting).

Spinal Cord Compression:

If the patient experiences spinal cord compression during the treatment period, the patient should be treated for the event, and this will be considered disease progression.

Surgical Intervention:

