8.3 Statistical and analytical plans: as above

8.4 Planned interim analyses: yearly at time of IND review

8.5 Determination of sample size

Dose escalation phase: 3 dose levels using standard 3+3 design (N=9)

Cohort expansion N=6

9. Data handling and quality assurance

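### The expansion safety rule acts only at the third DLT and is not reconciled with the escalation rules; the two conflict directly if the expansion opens on a tentative MTD

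*Combined protocol and SAP*

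**What the plan says.** Three rules bear on the same dose.

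- **Expansion (section 8.1, Safety monitoring rule).** The trigger is "Should DLTs occur in more than two patients at any time during the dose expansion phase". Its consequence is "No additional patients will be accrued until the data is reviewed and a decision is made to continue at the current dose" or to move the expansion to the prior dose, with the decision put in writing. The expansion has six patients (section 8.5: "Cohort expansion N=6").
- **Escalation (Dose Modification and Escalation, after section 6.2.9).** "If at least 2 patients are observed to have a dose-limiting toxicity (DLT), the MTD will have been exceeded", and enrolment at that level and above ends. After 1 DLT in the first three patients, three more are treated. If any of these has a DLT, "otherwise, the prior dose level is defined as the MTD".
- **Confirmation of the MTD (same place).** A dose with only three patients treated is a tentative MTD. "A tentative MTD becomes final when a total of 6 patients are treated with less than 2 showing DLT".

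The protocol does not say whether an MTD must be final before the expansion opens, whether DLTs from the two phases are added together, or whether the escalation rules still apply during the expansion.

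**The concern.** The expansion is there to firm up the dose that the primary objective asks for. Its rule acts at 3 of 6 (50%), while the rule that defines the MTD acts at 2 of 6 (33%). No reason is given for the difference.

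Where the expansion patients are also the ones who complete the six needed for a final MTD, the same data give two instructions. The escalation text says that the MTD is not final and that enrolment at the level ends. Section 8.1 asks for no meeting, no hold and no written decision. Site staff working from section 8.1 could go on enrolling at a dose that has just failed the plan's own confirmation criterion.

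**Working it through.** **Inputs.** Expansion size 6 and a trigger of 3 or more (sections 8.5 and 8.1). Final MTD requires at most 1 DLT in 6 (Dose Modification and Escalation). The protocol states no target or expected DLT rate and no operating characteristics for the section 8.1 rule, so there is no plan figure to reproduce. The true rate p below is an assumption, shown over a range, with patients treated as independent.

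**Step 1: can the expansion open on three treated patients?** The documents allow it. Section 8.5 sizes the escalation at 9 for three levels, which is three per level. The synopsis makes 50 kBq/kg the MTD if 75 kBq/kg gives 2 of 3 DLTs. Nothing requires final status first. Table 1 (8 patients at 100 kBq/kg, then a separate 6) and the synopsis (14 + 6) also leave room for a final MTD beforehand.

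**Step 2: the direct conflict.** Start from 0 of 3 in escalation. The rules diverge when exactly two of the next three patients have a DLT (three of three would trigger section 8.1). The probability is 3p²(1−p):

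- p = 1/3: 3 × 0.1111 × 0.6667 = 22%
- p = 0.40: 3 × 0.16 × 0.60 = 29%
- p = 0.50: 3 × 0.25 × 0.50 = 38%

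These are conditional on 0 of 3. Multiplying by (1−p)³ = 0.296, 0.216 and 0.125 gives 6.6%, 6.2% and 4.7%, before asking whether that dose is the one taken forward.

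**Step 3: the case without a conflict.** If six patients were already treated with 0 or 1 DLT, two expansion DLTs give 2/12 = 17% or 3/12 = 25% at the dose. If eight were treated, they give 2/14 = 14% or 3/14 = 21%. No passage says that these exceed the MTD.

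**Step 4: how often section 8.1 acts, given that the expansion is reached.** Exact binomial tails for six patients. The fourth column is the chance that the third DLT falls among the first five patients, so that at least one place is left to hold. The last column is the chance that such a dose passes 3+3, (1−p)³ + 3p(1−p)² × (1−p)³.

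| Assumed p | 3 or more of 6 (as written) | 2 or more of 6 | 3 or more of first 5 | Passes 3+3 |
|---|---|---|---|---|
| 10% | 1.6% | 11% | 0.9% | 91% |
| 20% | 9.9% | 34% | 5.8% | 71% |
| 33% | 32% | 65% | 21% | 43% |
| 40% | 46% | 77% | 32% | 31% |
| 50% | 66% | 89% | 50% | 17% |

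The fourth column is a best case. It assumes that each outcome is known before the next enrolment, whereas the DLT window is six weeks ("DLTs will only be monitored during the first 6 weeks of treatment") and no staggering is stated for the expansion.

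**The case against.** The strongest reply is that the criteria answer different questions. The 2-of-6 criterion declares an MTD during escalation. The expansion is described as a further step at a dose already accepted (section 1.1: "If well tolerated at the MTD, an additional 6 patients will be studied to better define toxicity"). If the MTD is final by then, two expansion DLTs are 2 or 3 in 12 to 14 patients. This stands, and it confines the direct conflict to an expansion that opens on three treated patients.

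A second reply is that nothing in section 8.1 suspends the escalation rules. If they still govern, 2 of 6 is already dealt with by ending enrolment; if they do not, there is no contradiction. This is a fair reading of each branch, but the protocol does not say which branch applies, and that is the defect.

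A third reply is that with no target rate stated, a trigger above an observed 33% is a design choice that the documents do not prove wrong. That also stands. Moreover, doses with high true rates often fail 3+3. The chance of passing it and then showing exactly 2 of 6 in the expansion is about 14%, 10% and 4% at 33%, 40% and 50% (0.43 × 0.33, 0.31 × 0.31, 0.17 × 0.23).

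A reader might infer that any 2-of-6 expansion result shows a dose above the MTD that then passes with no review at all. The documents do not support this. Step 3 of the working shows why the count alone is not enough. Section 9.2 requires a data review when the expansion is complete, section 8.4 a yearly analysis, section 7.4 reporting of serious and of unexpected, clinically significant grade 3 or 4 toxicity, and section 10 allows termination on safety findings. What is missing at two DLTs is the DLT-triggered meeting, hold and written decision.

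**Conclusion.** The point holds as an unreconciled threshold and a missing pooling rule. The conflict is direct in one situation that the documents allow: an expansion opened on a tentative MTD with 0 of 3 DLTs, followed by exactly two DLTs in the next three patients. Given that start, its probability is 22%, 29% and 38% at true rates of 33%, 40% and 50%. Once the expansion is reached, the written rule calls a review with probability 32%, 46% and 66% at those rates, and 3+3 lets such doses through about 43%, 31% and 17% of the time. All these figures rest on assumed DLT rates and independent patients. They do not show that any dose is too high, nor which of the rules is clinically right. The change should be made, because the expansion supports the primary objective and the correction is short.

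**What to change.** Reconcile section 8.1 with Dose Modification and Escalation. The text should:

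1. say whether the expansion may open on a tentative MTD, and whether the escalation rules continue to apply during it;
2. state that DLTs at the dose are counted across escalation and expansion;
3. state that any count which the escalation text says exceeds the MTD or bars a final MTD (two or more among the first six treated at that dose) also triggers the section 8.1 meeting, accrual hold and written decision;
4. for larger pooled totals, state a trigger scaled to the number treated. The 2-of-6 limit should not be carried over: with 12 pooled patients and a true rate of 10%, two or more DLTs occur with probability 1 − 0.9¹² − 12 × 0.1 × 0.9¹¹ = 34%.

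As a trigger, item 3 calls a review, not an automatic stop, and sets no dose. What follows from the escalation rules themselves is for the sponsor to settle under item 1.

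The cost is a short protocol amendment and an occasional extra meeting and pause. For two or more DLTs in six patients the chance is about 11% at a true 10% rate and 34% at 20%, against 1.6% and 9.9% for the present trigger. Starting from 0 of 3, two or more in the next three has probability 3p²(1−p) + p³, which is 2.8% and 10.4% at those rates. The cost of the scaled trigger depends on the limit that the sponsor chooses.
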